4b). Secondary Hypotheses - Although a study is usually based around a primary hypothesis, secondary hypotheses may also be pre-specified although based on outcomes of lesser importance or additional interest. As the primary hypothesis is usually the basis for statistical power calculations, secondary hypotheses with insufficient power will generally not lead to statistically robust conclusions.

RESPONSE: Externally mounted magnet systems will a) result in a significant improvement in the completeness of eye closure and opening as measured using image analysis of eye opening/closing with compared to without the device; b) will be comfortable to wear defined as a mean participant-reported comfort rating greater than or equal to 6/10 (or 60cm on a 100cm visual analog scale)

STUDY DESIGN

5) State the design of the research (e.g. randomized controlled study, cross-sectional survey, prospective or retrospective cohort/case-control).

**Whatever the study design, you need to ensure that you provide the reader with a clear statement and description of your proposed design. You may also explain why the particular study design has been chosen in preference to other possible designs (i.e. justification for choice of study design)*

RESPONSE: This is a prospective study. As the principal aim of this study is to determine safety and feasibility of extended home use, we will not attempt to randomize patients to a treatment and a placebo group nor will we have an age-matched control group. Participants will be made aware that a predicate device is commercially available and the magnet device is experimental.

ELIGIBILITY CRITERIA

6a). Inclusion Criteria - Inclusion criteria are the 'characteristics' that clearly describe the study population that are required for a subject to be included in the study. The criteria may be based on factors such as age, gender, the type and stage of a disease, previous treatment history, and co-morbid medical conditions. They may state appropriate criteria for admitting special 'at-risk' populations such as women of reproductive age, children or patients with disease states or organ impairment.

RESPONSE: Presence of an eyelid movement disorder for at least one eye, moderate cognitive function or better defined as greater than or equal to 18 out of 30 on a pre-screening of the Mini-Mental State Exam, age 5 or older

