6b. Exclusion Criteria - Provide details of participants that will be considered ineligible to participate and justification for their exclusion. These criteria are not always clinical in nature, aiming principally to accommodate participants in a safe and ethical manner. Criteria may include circumstances that interfere with the participant's ability to give informed consent (diminished understanding or comprehension, or a language other than English spoken and an interpreter unavailable), contraindications to the study treatment(s)/procedure(s), taking certain concomitant medication(s), or conditions that interfere with a patient's ability to comply with all treatment(s)/procedure(s).

RESPONSE: Absence of an eyelid movement disorder or presence of a corneal ulcer. Those with a corneal ulcer are at risk for permanent loss of vision and should be managed with proven methods. Age less than 5, Severe Cognitive impairment defined as MMSE score <18, behaviors consistent with delirium (combinations of disorientation, hallucinations, delusions, and incoherent speech), or lethargy. These individuals must be excluded since participation requires competent self-care, reliable responses and cooperation during fitting of the devices.

STUDY OUTCOMES

7a). Primary Outcome - The primary outcome should be the most important and clinically relevant outcome (e.g. clinical, psychological, economic, or other) of the study. This is the measure used to answer your study aim. However, it is also the outcome used to calculate study sample size and power and test the primary research hypothesis. Generally, no more than 1-2 primary outcome measures are pre-specified. Primary outcome measures may be measured in various ways such as: binary (e.g. caesarean/no caesarean, blood loss $\geq 500\text{mL}$ /blood loss $< 500\text{mL}$); continuous (e.g. weight - kg, blood loss - mL); ordinal (e.g. pain - mild, moderate, severe); time to event (e.g. survival), and counts (e.g. number of infections, number of events occurring).

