spectacle mounted magnet may also be used for lagophthalmos (mounted within the inferior eye-wire to pull the upper lid down). In this scenario there is no lower lid array. **20 MINUTE TRIAL:** For both the ptosis and lagophthalmos magnet devices: If experimenter likert-type scale score is greater than or equal to 6 on the blink mechanics and efficacy and better than 8 on the skin integrity and the participant rated comfort is greater than or equal to 5/10 on likert-type or 50mm or better on a 100mm Visual Analog Scale and they express a desire to continue wearing the device, they will be offered participation in an extended 20 minute trial. This is followed by a repeat of the visual acuity, slit lamp exam, video and rating scale data collection. **EXTENDED 1-WEEK TRIAL:** Participants who have a successful 20 minute magnet device trial defined as an Examiner Rating Scale score of greater than or equal to 6 on the blink mechanics and efficacy, better than 8 on the skin integrity, participant rated comfort greater than or equal to 5/10 (or 50mm on a 100mm Visual Analog Scale), and express a desire to continue wearing the device will be offered participation in an extended 1-week trial. These cut-offs were based on observations during the pilot study at Spaulding (see manuscript attached) where patients who reported a desire to wear the device typically rated their comfort and satisfaction at this level or better. The PI or other trained study staff supervised by the PI will train the patient how to apply and remove the lid magnet; similar to what is done for insertion removal of contact lenses. They will be trained how to place on the secondary magnet spectacles to sit in the correct position on their face. If the participant is able to successfully demonstrate the ability to do this, only then will the magnet device be dispensed home with the patient (see exception* below). During each 1-week during the extended trial, the participant will be advised (instructional sheet sent with the participant) to wear the device as much as they would like up to 8 hours per day in the case of ptosis and 24 hours per day for lagophthalmos so long as comfort remains 5 or better (see participant instructions). Participants will be asked to document their wear time and assess their comfort on a 10-pt scale (10 being best) on a regular (min. daily) basis. For lagophthalmos, the device ideally will be worn 24 hours/day. For ptosis, the magnet glasses will be removed at night, and the lid magnet will remain attached to the eyelid. The participant may shower/wash face with the lid magnet on as the Tegaderm is not critically bothered by water and the magnet is encased in PDMS. They will be advised not to submerge the device (i.e. swim with the device on). Lid magnets will be removed and applied as they start to become detached (typically 2-3 days). If self-assessed comfort is worse than 5/10 or if the intervention fails (eg. stops working or falls off and cannot be reapplied) the participant will be instructed to contact the PI directly. The PI will advise if the device should be removed, and will come to MEEI or Schepens within 24 hours of the complication to evaluate the problem. If there is a problem requiring immediate attention, the participant will be advised to seek attention in the MEEI EW. **AT A 1-WEEK FOLLOW-UP** study appointment we will repeat visual acuity, slit lamp, rating instruments and video recording. **SAFETY CUTOFFS:** The participant's study status will change to suspended and an adverse event reported to the IRB with any of the following findings at the follow-up or any emergency visit: Any broken skin, decrease in visual acuity more than 2 lines, worsening of corneal rating of more than 1.5 points or other ocular surface ratings more than 2 points, and comfort rating lower than 5/10 (or 50cm on the 100cm visual analog scale). The extended trial of the magnet device may be renewed 3 times (for a total of 1 month with weekly visits) as long as the above mentioned criteria continue to be met. If still safe/effective at 1 month, the participant will be given the option to take the device home for an additional 1 month. The device trial/study ends after 8-weeks (4 weekly trials followed by a 1-month trial) or with failure/complication or voluntary withdrawal. If the device is successful over the duration of the study and the participant would like to continue wearing it, a clinical decision will be made as to if and for how long per day it should be worn. This is justified when there appears to be no other equivalent treatments which may be substituted. It would not be ethical to retract the device from a participant if it is working and there is no other comparable option. In such cases, the participant will return 1 month later for an additional follow-up evaluation prior to turning the maintenance of their care over to the neuro-ophthalmology, oculoplastics, or vision rehabilitation service. Their specialist will continue to monitor for complications after the study if the patient keeps the device. The study will end when 25 participants in each group have completed the study (~2yrs). **EXCEPTION* TO TRAINING REQUIREMENT:** If the participant is unable to apply and remove the device themselves (physical or cognitive limitations) and/or they have cognitive impairment (MMSE 20-23), they may still participate in an extended 1-week trial if the following criteria are met: 1) a caregiver is able to be trained to apply/remove the device, 2) The primary caregiver assures 24-hour supervision (see form on the last page of the "instructions for use document"), 3) The cognitively impaired participant (or participant who cannot apply the device themselves) agrees to attend daily study visits for the first

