
week of the extended trial. If there are no complications after 1-week, a clinical decision may be made by the PI to decrease the visit frequency to the standard protocol.

9) Randomization (if applicable)

Include the method (including any software) used to generate the random allocation sequence. Describe type of randomization performed, ratio of assignment to groups, block size permutation and stratification if applicable. Explain the methods used to conceal group allocation until assignment. Also, include information on who will generate the allocation sequence and who will assign participants into their groups.

This section should also discuss if participants, the investigator, and those assessing/analyzing the outcome(s) will be blind (or masked) to group assignment or if the study will be an open-label study (investigators and subjects know their assigned group).

RESPONSE: There is no randomization counterbalancing will be used given the small sample size.

10) Study Specific Procedures: List all procedures (interventions, tests, surveys, etc.) to be performed ONLY for research purposes

RESPONSE: Specific to the study are the high magnification photo analyses of skin integrity, participant comfort and satisfaction ratings (visual analog scales), video analyses of the eyelid movements to measure the change in the amount of eye-opening and closing (volitional and reflexive opening and closing) with the magnetic devices compared to no device, comparisons of the amount of opening and closing with the magnetic devices compared to with the ptosis crutch or external lid weights, and efficacy ratings by both the clinician and participant.

11) Standard of Care Procedures: Clearly list all standard of care (standard therapy) procedures (interventions, tests, etc.) to be performed regardless of the subject's enrollment in the study, but that will be included in the research assessment.

RESPONSE: NA

MEASUREMENT TOOLS

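### The home-use exception applies its extra safeguards by cognitive score only at MMSE 20-23, so eligible participants scoring 18-19 who can self-apply get less protection than less impaired ones

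*Combined protocol and SAP*

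**What the plan says.** **Eligibility.** Section 6a admits participants with "moderate cognitive function or better defined as greater than or equal to 18 out of 30" on the MMSE. Section 6b excludes "Severe Cognitive impairment defined as MMSE score <18", on the ground that "participation requires competent self-care, reliable responses and cooperation during fitting of the devices".

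**Bands.** Section 8 treats a screening score of 18-23 as mild impairment and asks such candidates to come back with a caregiver. Section 12 repeats the bands: none 24-30, mild 18-23, severe 0-17.

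**Ordinary home-use rule (Section 8).** The participant must show that they can apply and remove the device, and "only then will the magnet device be dispensed home with the patient". This rule carries no MMSE condition.

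**Exception (Section 8).** It has two triggers joined by and/or. The first is ability: "If the participant is unable to apply and remove the device themselves (physical or cognitive limitations"). The second is score: "they have cognitive impairment (MMSE 20-23), they may still participate in an extended 1-week trial". Three conditions follow: a caregiver who can be trained, that caregiver's assurance of 24-hour supervision, and daily attendance, worded as "The cognitively impaired participant (or participant who cannot apply the device themselves) agrees to attend daily study visits for the first" week. If that week passes without complications, "a clinical decision may be made by the PI to decrease the visit frequency to the standard protocol".

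**The concern.** Every other cognitive threshold in the plan has 18 as its lower bound, and only the exception uses 20. The scores left out are the two lowest that the trial admits, so the omission falls on the most impaired eligible participants.

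This matters because of how safety is monitored at home. The Background says the earlier ptosis participants were inpatients under round-the-clock supervision who wore the device for up to 2 hours a day, and that this is the first study to send the device home. Wear now extends to 8 hours a day for ptosis and 24 for lagophthalmos. Between visits the participant has to judge comfort, log it, and contact the investigator if comfort drops below 5/10 or the device fails. Loss of acuity and corneal worsening, which are among the suspension cutoffs, are assessed only at a follow-up or emergency visit. Those who may be least reliable at self-monitoring would have the longest interval between scheduled examinations.

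**Working it through.** No sample-size, power or error-rate figure is involved. The check compares score ranges and then counts scheduled visits.

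**Inputs**

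| Item | MMSE range | Where |
|---|---|---|
| Eligible | 18-30 | Sections 6a, 6b |
| Mild impairment | 18-23 | Sections 8, 12 |
| Exception, ability trigger | any eligible score | Section 8 |
| Exception, score trigger | 20-23 | Section 8 |
| Ordinary dispensing rule | no score condition | Section 8 |

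**Step 1: scores missed by the score trigger.** Eligible and mildly impaired = {18, 19, 20, 21, 22, 23}, six scores. Score trigger = {20, 21, 22, 23}, four scores. Difference = {18, 19}, two scores.

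**Step 2: who is affected.** The ability trigger has no score limit, so participants at 18-19 who cannot self-apply are already covered. The gap is confined to those at 18-19 who pass the demonstration.

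| Participant | Passes demonstration | Cannot self-apply |
|---|---|---|
| MMSE 18-19 | Standard schedule | Exception conditions |
| MMSE 20-23 | Exception conditions | Exception conditions |
| MMSE 24-30 | Standard schedule | Exception conditions |

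In the first column, the 18-19 group is handled like the unimpaired group, and the milder 20-23 group is handled more strictly than either.

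**Step 3: first-week visits.** Daily visits give 7 in the week, and the standard schedule gives 1 (the 1-week follow-up). The difference is 7 - 1 = 6 per participant. The longest gap between scheduled examinations is 7 days on the standard schedule and 1 day under the exception.

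**Step 4: total visits if the gap is closed.** The plan gives no MMSE distribution, so the number affected, k, is an assumption. Extra visits = 6k: for k = 0, 1, 2 and 5 of the 50 participants, that is 0, 6, 12 and 30.

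**The case against.** The mismatch in the numbers is not in dispute. The case against concerns what follows from it.

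- **The investigator may have meant to keep 18-19 out of home use.** The exception is permissive, so 20-23 could be read as the range allowed home. On that reading the lowest scorers are more protected, and the rule is ambiguous, not reversed. But no text states such a bar, the ordinary rule has no score condition, and the ability trigger lets in any eligible score. It would be odd to admit someone at 18 who cannot apply the device and refuse someone at 18 who can.
- **The clause is headed as an exception to training, so someone at 22 who passes the demonstration may not need it.** The heading gives this some support. The and/or wording does not, because it makes the score a trigger in its own right. Condition 3 also names the cognitively impaired participant separately from the one who cannot apply the device.
- **Condition 3 gives no score, so staff might extend the safeguards to 18-19 anyway.** They might, since Section 12 counts those scores as mild impairment. That suggests the 20 is a drafting slip, but it leaves staff to settle the conflict themselves.
- **A caregiver is already requested at 18-23.** This is correct and deserves mention. The request applies around screening and consent, however, and requires no caregiver training, home supervision or daily visits. It also shows that the plan handles 18-23 as one group elsewhere.
- **Few people are affected.** This is probably right. They must score 18 or 19, meet the 20-minute trial criteria and demonstrate self-application. It limits the size of the problem but does not make the threshold right.

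**Conclusion.** The concern holds. As written, the score trigger covers 4 of the 6 eligible mild-impairment scores and omits the two lowest. Participants at 18-19 who can self-apply go home under the standard safeguards: training, instruction sheet, daily comfort log, contact with the investigator, weekly visits and suspension cutoffs. Those at 20-23 with the same ability get these plus a trained caregiver, 24-hour supervision and 6 more visits in the first week.

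This conclusion rests on reading and/or literally and on the absence of any rule barring 18-19 from home use. On the alternative reading, eligible participants are shut out of home use without the plan saying so, and the sentence still needs correcting. The number affected cannot be estimated from the plan. No statistical quantity changes. The point should be fixed because it concerns a wrong threshold in a participant-safety rule.

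**What to change.** In the Section 8 exception to the training requirement, change the MMSE range from 20-23 to 18-23. Every eligible participant classed as mildly impaired then faces the same home-use conditions, and the sentence agrees with Sections 6a, 6b and 12 and with the screening text in Section 8. No other section needs to change. Under the rules as written, the edit only adds safeguards. If the investigator did intend to keep 18-19 out of home use, the protocol should say so explicitly instead.

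The cost is one number in one sentence. Each newly covered participant needs a trained caregiver, 24-hour supervision and 6 more first-week visits. If 0 to 5 participants were affected (an assumption), that is 0 to 30 extra visits in total. A participant at 18-19 with no available caregiver could not enter the home trial.

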RESPONSE: Aim 1: Determine the safety and feasibility of externally mounted magnetic devices for extended (> 1 week) home use for the management of early post-acute and chronic eyelid movement disorders. Aim 2: Collect preliminary data on the efficacy of external magnetic eye lid devices stemming from a variety of different pathologies.

OBJECTIVES

3) Your focused research question needs to be further refined into one or more study objectives. The study objective(s) should be single and quantifiable statement(s) that will allow you to answer your research question.

RESPONSE: Objective 1: Determine the safety and feasibility of externally mounted magnets for extended management of chronic eyelid movement disorders by measuring visual acuity and corneal and skin integrity and comfort over 8 weeks of wear.

HYPOTHESES

4a). Primary Hypothesis - Hypotheses are more specific than objectives and amenable to statistical evaluation. Your primary hypothesis is your statement of the hypothesized effect on the primary outcome measure. A hypothesis is worded very simply and written as 'testable' statements. Your experimental results will prove or disprove your hypothesis. Hypotheses are generally stated in the null form (H_0) as they have their basis in inferential statistics. Rejecting the null hypothesis increases our confidence, with a given level of probability, that there is a relationship between the variables being studied. However, a classic scientific hypothesis includes both a null and alternative (H_a) hypothesis.

**e.g. H_0 : Asthma prevalence rates are not different among children from low and high socioeconomic groups in Istanbul. H_a : Asthma prevalence rates are different among children from low and high socioeconomic groups in Istanbul.*

RESPONSE: Hypothesis: Externally mounted magnet systems will have a good safety profile defined as a mean decrease in visual acuity 1 line or less, high-mag photo documented skin-integrity rating better

than 2 (FDA industry scale), and no more than a two grade (NEI/Industry Workshop scale (Lemp, 1995)) worsening in superficial punctate keratitis on high mag photo-documented analysis.

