RESPONSE: Skin integrity scales, change in ocular surface staining rating, participant comfort and satisfaction rating, and change in visual acuity. Skin integrity will be analyzed by applying a likert-type rating system to a high-mag/high-resolution photo documented image of the subject's lid skin. The number of adverse events will also be reported, defined as incidents which require temporary or permanent suspension of the participant's involvement. These include any broken skin, decrease in visual acuity more than 2 lines, worsening of corneal rating of more than 1.5 points or other ocular surface ratings more than 2 points, and comfort rating lower than 5/10 (or 50cm on the 100cm visual analog scale).

7b). Secondary Outcome(s) - Secondary outcome(s) are measures of additional or less important research interest. They may include additional clinical, psychological, economic, or safety outcomes (e.g. treatment related side effects/adverse events). However, as these endpoints are not used to calculate study power and sample size it is often not possible to draw robust conclusions from the results.

RESPONSE: Video analysis of eyelid biomechanics to measure the completeness of eye closure and opening compared to 1) no device, 2) relative to the contralateral side (if normal), 3) relative to the ptosis crutch or external lid weights. The same paired comparisons will be performed for the clinician and participant rating scale data. 3) Cognitive score on the MoCA will be analyzed for relationship to length of time in the study and satisfaction rating scores).

STUDY PROCEDURES

8) In this section you need to clearly and comprehensively describe exactly what will happen to participants once they are enrolled in your study. Depending on the study it might include how potential participants will be approached, when they will be randomized, the frequency and duration of visits or whether they are expected to self-complete a daily diary at home, the duration of the study or follow-up, and any measurements taken at each visit (e.g. questionnaires, physical measurements, biological samples).

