impairment (24-30), Mild (18-23), and severe 0-17) (Tombaugh et. al 1992). Once in the study, the Montreal Cognitive Assessment MoCA will be administered, which is a slightly longer and more sensitive test battery for detecting and quantifying cognitive impairment (see http://www.mocatest.org/normative_data.asp). Any study staff administering the cognitive tests will be trained and practiced in using the standardized instructions (attached). The Visual functioning questionnaire (VFQ-25) is a validated survey and will be self-administered by the participant. Visual acuity will be collected using eye charts available in the services involved in a calibrated exam lane with controlled lighting. Participants will be tested on the same chart at every visit. IMAGE CAPTURE: All devices will be registered with MEEI. Video data collection may be done with the PI's iPhone (which is registered with MEEI and password protected) or a high resolution video recording device (yet to be purchased) and a digital SLR camera. The PI will personally collect this data. Any such device will be registered and compliant with MEEI safe computing policies. All data will be immediately transferred and removed from the image acquisition device. Use of USB drives will be avoided, but if necessary will be encrypted/protected consistent with MEEI policies. All effort will be made to only capture the eyes in a manner which would prevent identification of the participant from the images. RATING SCALES: We are using the ocular surface quantification method endorsed by the NEI (NEI/Industry Workshop scale (Lemp, 1995)). We are aware of no validated instruments for the other subjective measurements needed (skin integrity, comfort and efficacy of devices). We will use a well-accepted method of subjective rating (Likert-type rating scales), scored on a 10-point scale. Skin integrity will be rated by the clinician at the time of the study visit, and later by an independent rater (prior to publication) using the photos/video using a likert-type scale. Additionally we will evaluate the use of a visual analog-type rating scales (not used in our previous work). The visual analog scale method allows a continuous measure of subjective response which simplifies analysis. Study staff will read the rating scale instructions word for word (see recording forms, attached).

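### Skin integrity, a primary outcome, is scored by two raters; the plan does not specify masking of the independent rater to visit, nor say outright which rating is analysed

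*Combined protocol and SAP*

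**What the plan says.** All references are to numbered items of the combined protocol and SAP.

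- **Item 7a (Primary Outcome)** lists "Skin integrity scales, change in ocular surface staining rating, participant comfort and satisfaction rating, and change in visual acuity". Skin integrity is to be analysed by "applying a likert-type rating system to a high-mag/high-resolution photo documented image" of the lid skin.
- **Item 4a (Primary Hypothesis)** includes a photo-documented skin rating among its three safety criteria.
- **Item 10 (Study Specific Procedures)** lists high-magnification photo analysis of skin integrity as a research-only procedure.
- **Item 12 (Measurement Tools, rating scales)** says that the authors know of no validated instrument for skin integrity and will use a 10-point Likert-type scale. The clinician gives one score during the visit. A second score is given "later by an independent rater (prior to publication) using the photos/video using a likert-type scale".
- **Item 8 (Study Procedures)** uses an examiner skin score "better than 8 on the skin integrity" as one condition for moving to the 20-minute and 1-week trials.
- **Item 14 (Statistical methods)** plans a mean rating for skin and a repeated-measures ANOVA for change across visits.
- **Item 9 (Randomization)** carries a form prompt asking whether those assessing outcomes will be masked. The response covers only randomization and counterbalancing.

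**The concern.** The study has no placebo or control group (item 5), so any difference in how strictly skin is scored at different visits goes straight into the estimated change across visits. The scale is subjective and unvalidated, which leaves room for such a difference. The clinician necessarily knows the visit, and also knows that the score counts towards continuation. The independent rater is a real safeguard against the clinician's own leanings. But independence from the clinician is not the same as being unaware of which image is early and which is late, and the plan does not address that.

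Two scores will exist for the same skin. If the one to be analysed is not fixed beforehand, the choice can be made after both are seen. At stake is whether the reported course of skin integrity over 8 weeks can be trusted. In a safety study, lenient late scores that hide real worsening would be the more serious error.

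**Working it through.** **1. Which rating is analysed?** Items 4a, 7a and 10 all describe a photo-based skin outcome. Item 12 ties photos and video to the independent rater and the visit assessment to the clinician. Together they make the independent photo score the natural reading. That remains an inference: item 7a does not say who scores the image, item 12 does not rank the two ratings or say how disagreement is handled, and item 14 refers to a mean skin rating without naming its source.

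**2. What does each rater know?** The clinician knows the visit. For the independent rater, no section says whether visit, date or the clinician's score is visible, or in what order images are scored. The form prompt in item 12 asks about inter-rater reliability; the response gives no plan for it.

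**3. Does knowledge of visit matter for the planned analysis?** Take two visits. Let δ be the true mean change in skin score, b the difference in scoring strictness between the visits, and SD the standard deviation of the change score. The expected observed change is δ + b. Without a control group, nothing in the design separates b from δ.

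**4. How sensitive is such a comparison?** The plan has no figure to reproduce, because item 13 declines a power calculation for the primary outcome. The following is an illustration on assumed inputs, not an estimate.

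- n = 25 (one condition) or 50 (both), from item 8, assuming every participant contributes both ratings.
- Paired t-test, two-sided 0.05, a two-visit simplification of the ANOVA.
- No true change, δ = 0.
- b/SD is assumed, from 0.1 to 0.5.
- The rejection rate comes from the noncentral t distribution with n − 1 degrees of freedom and noncentrality √n × (δ + b)/SD.

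For example, n = 25 and b/SD = 0.2 give noncentrality 5 × 0.2 = 1.0 and a rejection rate of 16%.

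| b/SD (assumed) | n = 25 | n = 50 |
|---|---|---|
| 0.1 | 8% | 11% |
| 0.2 | 16% | 28% |
| 0.3 | 30% | 55% |
| 0.5 | 67% | 93% |

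The reverse case follows from the same formula. At n = 25, unbiased scoring would detect a true worsening of 0.5 SD in 67% of studies. If a lenient shift of the same size offsets it, δ + b = 0 and the rate falls to 5%.

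The documents give no SD for the skin score and no size or direction for b, so no row of the table can be picked as the applicable one.

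**The case against.** The strongest reply is that the plan already does most of what is needed. It has an independent rater working from images, and three items describe the outcome as photo-based. Also, item 13 addresses the primary hypothesis through the proportion of participants with a safety issue and the proportion completing. If a safety issue means the adverse events of item 7a, the skin trigger is broken skin, a present-or-absent finding and not a 10-point score. Both points stand. They limit the consequence to the mean rating and the test across visits, but they do not settle who scores the analysed image or what that person knows.

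Four stronger readings are tempting and are not supported:

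- **That the independent rater is unmasked.** The plan is silent; it does not say that the rater sees visit labels or chronological order. The statement "The PI will personally collect this data" concerns image capture, not scoring.
- **That a small shift would carry the study mean over 8.** The criterion of better than 8 applies to individual participants for continuation; no analysis compares a mean with it. The skin threshold in item 4a is on a different scale, in the words "than 2 (FDA industry scale), and no more than a two grade".
- **That the same remedy covers corneal staining at no extra work.** Item 12 plans an independent rater for skin only.
- **That masked scoring costs nothing.** The documents give no cost, and images must be coded and reordered. The clinician's rating also serves decisions made at the visit, so later scoring cannot simply replace it.

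**Conclusion.** The point holds in a limited form. A subjective, unvalidated primary outcome is scored twice. Masking to visit and to the other rater's score is not specified, and the rating to be analysed can be inferred but is not stated. Knowledge of visit could bias the analysis across visits in either direction. The size is unknown, and the table above shows only that modest shifts relative to the SD would matter at the planned numbers. The conclusion rests on item 14's analysis across visits being carried out on one of these two ratings. This is more than a missing detail, because a concrete change would reduce bias in a planned analysis.

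**What to change.** Cheap improvement, a few sentences in items 7a, 12 and 14:

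1. Name the independent photo rating as the analysed skin integrity outcome, and say that it feeds the mean and the repeated-measures ANOVA.
2. Have that rater score coded images from all visits in random order, without visit, date or the clinician's score.
3. Keep the clinician's same-day rating for the visit decisions the plan already contains.
4. Report agreement between the two ratings.

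When making the edit, reconcile the skin scale named in item 4a with the 10-point scale in item 12, so that the analysed score and its criterion refer to the same instrument. Confirm also that a usable lid-skin image is taken at each analysed visit: item 8 names video recordings at baseline and follow-up but no skin photograph.

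The cost is a small effort to code and shuffle images; the rater and the photo analysis are already planned. Masking may be incomplete where traces of the device or adhesive are visible, and the report should say so.
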